8.6 Rescue Therapies

Subjects may receive rescue therapy at the discretion of the Investigator if there is an urgent need to increase platelet count, such as in the case of life-threatening thrombocytopenia, in the opinion of the Investigator, clinical signs and symptoms suggesting a potential bleed (e.g., wet purpura) or a major bleed. All rescue medications, including dose and frequency, must be recorded on the eCRF.

Rescue therapy may include:

- The addition of any *new* ITP medication or medication to treat thrombocytopenia, such as:
 - Corticosteroids
 - o IVIg
 - o Anti-D
 - Platelet transfusion
- Any *increase in the Day 1/Visit 2 dose* of a concomitant ITP medication.
- TPO-RAs are not allowed as rescue therapy.

9 STUDY ASSESSMENTS AND PROCEDURES

A schedule of events in tabular format is provided for the Core Phase in Table 7 and for the Extension Phase in Table 8 in Appendix A.

9.1 Core Phase

9.1.1 Informed Consent/Assent

As AVA-PED-301 is enrolling adolescents and children as subjects, the study site should follow the guidelines from their respective IRB/IEC to determine the requirements for parental/LAR consent and child assent.

The ICF/assent form must be signed and dated prior to the initiation of study-related assessments, and prior to administration of study drug. The original signed ICF/assent form for each participating subject will be filed with records kept by the Investigator. A copy of the ICF/assent form must be provided to the subject and/or the subject's LAR, as applicable.

9.1.2 Screening (Visit 1/Day -28 to -1)

The Screening Visit must be completed within 28 days of Day 1/Visit 2.

The following procedures will be performed at the Screening Visit.

- Collect signed and dated informed consent/assent prior to any study procedures.
- Review of inclusion/exclusion criteria (Section 6.1) to confirm study eligibility.
- Record subject demographic information.
- Record medical/medication/surgical history to include all past significant illnesses and/or surgeries (in the opinion of the Investigator) and all medications taken (including non-prescription medications, vitamins, dietary supplements, and herbal products) within the past 90 days.
- Record ITP history, including date of diagnosis and any concomitant ITP medications.
- Collect height and weight to determine BMI (calculated by eCRF).
- Perform abbreviated physical exam (PE). The abbreviated PE will consist of the following: general appearance, head, neck, eyes, ears, nose, throat, chest, lungs, heart, abdomen, extremities, joints, lymph nodes, and neurology.
- Collect vital signs (blood pressure, heart rate, and temperature). Vital signs should be taken after sitting for 5 minutes, whenever possible, and prior to any blood draws.
- Collect blood for clinical laboratory tests to assess study eligibility as outlined in Section 6 (see details in Section 9.5 and Core Phase Schedule of Events, Table 7).
 - Local laboratories may be used to confirm study eligibility, however, for study analysis and reporting purposes, only values determined at a central laboratory will be used with the exception of platelet count (Section 9.5).
- Collect blood for platelet count (local laboratory).

- o The platelet count obtained at the Screening Visit/Visit 1 and 1 other platelet count taken within 28 days on either side of the Screening Visit (may use a historical value collected per standard of care if within 28 days of Screening) will be averaged to obtain the study eligibility platelet count value, which must be <30×10⁹/L. The 2 samples must be obtained ≥24 hours and ≤28 days apart and the results must be available prior to randomization.
- Perform urine or serum pregnancy test for female subjects of childbearing potential. The pregnancy test may be performed locally.
- Review and record AEs that may have occurred after signing informed consent/assent.
- Discharge subject from clinic with instructions for when to return for Day 1/Visit 2.

9.1.3 Baseline (Visit 2 [Day 1])

Visit 2 should take place within 28 days of the Screening Visit. The first dose of study drug will be administered in clinic during this visit.

The following procedures will be performed at Day 1/Visit 2:

Prior to Dosing with Study Drug:

- Review of inclusion/exclusion criteria (Section 6.1) to confirm continued study eligibility.
- Perform WHO Bleeding Scale Assessment (Appendix C). The Investigator should ask the subject and/or the subject's parent/caregiver the following question: "Have you had any bleeding or bruising within the last 7 days?". This assessment should be completed prior to other visit assessments.
- Update subject demographic information, including age, if applicable.
- Review and document in the eCRF any changes since Screening to medical/medication/surgical history (including non-prescription medications, vitamins, dietary supplements, and herbal products).
- Review and document in the eCRF any changes since Screening to ITP history, including concomitant ITP medications.
- Collect weight to determine BMI (calculated by eCRF).
- Perform abbreviated PE. The abbreviated PE will consist of the following: general appearance, head, neck, eyes, ears, nose, throat, chest, lungs, heart, abdomen, extremities, joints, lymph nodes, and neurology.
- Collect vital signs (blood pressure, heart rate, and temperature). Vital signs should be taken after sitting for 5 minutes, whenever possible, and prior to any blood draws.
- Collect blood for clinical laboratory tests to assess study eligibility as outlined in Section 6.1 (see details in Section 9.5 and Schedule of Events, Table 7).
- Collect blood for platelet count (local laboratory).
 - The platelet count obtained at the Screening Visit/Visit 1 and 1 other platelet count taken within 28 days on either side of the Screening Visit (may use a historical value collected per standard of care if within 28 days of Screening) will be averaged to

- obtain the study eligibility platelet count value, which must be $<30\times10^9$ /L. The 2 samples must be obtained ≥24 hours and ≤28 days apart and the results must be available prior to randomization.
- o If the Visit 2 platelet count will not be 1 of the 2 platelet counts used to determine study eligibility, it should still be collected and the result recorded in the eCRF.
- Perform urine or serum pregnancy test for female subjects of childbearing potential. The pregnancy test may be performed locally.
- Randomize subject in the IRT system.
- If subject is in Cohort 3, randomize in the IRT system to the PK timepoint to be drawn at Visit 4 (Week 2) and Visit 12 (Week 10).
- After all previous assessments have been completed, administer study drug in the clinic, with food, at the dose and formulation described in Section 1.1.5.

After Dosing with Study Drug:

- Record date and time of the dose of study drug as well as the vehicle (including volume) used with the powder for oral suspension, if applicable, on the Dosing Diary.
- Administer Palatability Questionnaire within 2 minutes after the dose of study drug (Appendix B) to subjects in Cohort 3 who received the powder for oral suspension formulation and the Acceptability Questionnaire to their parent/caregiver.
- Collect vital signs (blood pressure, heart rate, and temperature) 30 minutes (±15 minutes) after dosing with study drug. Vital signs should be taken after sitting for 5 minutes, whenever possible, and prior to any blood draws.
- Dispense remaining 1-month supply of study drug for the subject to take at-home with instructions for administration.
- Dispense new Dosing Diary for the subject to take home with instructions for completion.
- Record any AEs.
- Review and record any concomitant medications, including any modifications to or new concomitant ITP medications.
- Discharge subject from clinic with instructions for when to return for Visit 3.

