3.2 Alternative Primary Efficacy Endpoint

Platelet response as defined by the proportion of subjects for whom at least 2 consecutive platelet assessments are $\geq 50 \times 10^9 / L$ over the 12 week Treatment Period in the Core Phase in the absence of rescue medication.

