4.1.1.1 Screening Period

The Screening Visit (Visit 1) will be completed within 28 days prior to Baseline (Day 1/Visit 2).

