4.1.1.2 Treatment Period (Visit 2 Through Visit 14)

Enrollment will begin with Cohort 1 (ages ≥ 12 to < 18 years). Enrollment into Cohort 2 (ages ≥ 6 to < 12 years) and Cohort 3 (ages ≥ 1 to < 6 years) will begin after notification from the Sponsor as described in Section 4.1 and Figure 2. Subject age at the time of randomization will be used.

At Day 1/Visit 2 eligible subjects will be randomized 3:1 to receive either avatrombopag or placebo at the starting dose determined by the PK/PD modeling described in Section 1.1.5. Throughout the Treatment Period, the dose of avatrombopag may be titrated up or down by the Investigator, based on platelet count (Table 4).

Subjects may be removed from the Core Phase and directly enrolled into the open-label Extension Phase due to a lack of treatment effect (Section 5.3).

Blood samples for serial PK assessments will be collected during Visit 4 (Week 2) and Visit 12 (Week 10) of the Core Phase. During these visits, subjects ≥6 years of age will have a blood sample drawn pre-dose and between 2 to 4 hours, 6 to 8 hours, and 10 to 12 hours post-dose (4 samples drawn at each visit, 2 mL each). Subjects <6 years of age will have a blood sample drawn pre-dose and at 2 to 4 hours post-dose but will be randomized in a 1:1 ratio, stratified by treatment group, to either the 6 to 8 hour or the 10 to 12 hour post-dose timepoint at Visit 4 (Week 2). The timepoint not drawn at Visit 4 (Week 2) will be drawn at Visit 12 (Week 10) (3 samples drawn at each visit, 2 mL each). For all age groups, blood samples for sparse PK assessments (2 mL each) will be collected while the subject is at the clinic during Visit 3 (Week 1) and at each visit during Visit 5 to Visit 11 (Week 3 to Week 9; 8 samples, 2 mL each) (Section 9.6).

After Visit 14 (Week 12), the subject may enter the 2-year open-label Extension Phase (Section 9.2). If the subject does not enter the Extension Phase, an End of Study Visit (Section 9.1.16) must be completed approximately 30 days after the last dose of study drug, prior to discharging the subject from the study. Visit 14 will serve as the last visit of the Core Phase and the first visit of the Extension Phase (Visit E-1).

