6.1 Inclusion and Exclusion Criteria for the Core Phase

6.1.1 Inclusion Criteria

Subjects who meet all of the following criteria will be eligible to participate:

- 1. Male or female subjects ≥ 1 and ≤ 18 years of age at Screening and Baseline.
- 2. Subject and/or subject's LAR must be able to provide informed consent and/or assent, as applicable.
- 3. Subject has a confirmed diagnosis of primary ITP according to the International Consensus Report on the Investigation and Management of Primary ITP (Provan, 2019) for ≥6 months duration and has had an insufficient response to a previous treatment, in the opinion of the Investigator.
- 4. Subject has an average of 2 platelet counts $<30\times10^9/L$ with no single count $>35\times10^9/L$.
 - The platelet count obtained at the Screening Visit/Visit 1 and 1 other platelet count taken within 28 days on either side of the Screening Visit (may use a historical value collected per standard of care if within 28 days of Screening) will be averaged to obtain the study eligibility platelet count value, which must be $<30\times10^9$ /L. The 2 samples must be obtained ≥24 hours and ≤28 days apart and the results must be available prior to randomization.
- 5. Subjects being treated chronically with corticosteroids or azathioprine/6-mercaptopurine must be receiving a stable dose for at least 30 days prior to Day 1/Visit 2 or must have completed these therapies more than 30 days prior to Day 1/Visit 2.
- 6. Subjects being treated with mycophenolate mofetil (MMF), cyclosporine (CsA), sirolimus, or danazol must be receiving a stable dose for at least 90 days prior to Day 1/Visit 2 or must have completed these therapies more than 30 days prior to Day 1/Visit 2.
- 7. Previous therapy for ITP with immunoglobulins (IVIg and anti-D) or corticosteroid rescue therapy must have been completed at least 14 days prior to Day 1/Visit 2.
- 8. Cyclophosphamide and vinca alkaloid regimens must have been completed at least 30 days prior to Day 1/Visit 2.
- 9. Splenectomy and rituximab must have been completed at least 90 days prior to Day 1/Visit 2.
- 10. Previous therapy with any other TPO-RAs (e.g., eltrombopag or romiplostim) or recombinant human TPO must have been completed 28 days prior to Day 1/Visit 2.

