4.3 Definition of Baseline

4.3.1 Baseline Platelet Count

In the efficacy analysis, baseline platelet count is the average of the platelet count obtained at the Screening Visit/Visit 1 and 1 other platelet count taken within 28 days on either side of the Screening Visit (may use a historical value collected per standard of care if within 28 days of the Screening Visit). The 2 samples must be obtained \geq 24 hours and \leq 28 days apart and the results must be available prior to randomization. This baseline platelet count will also be used as the stratification factor.

In the safety analysis, baseline platelet count is defined as the most recent non-missing measurement prior to first dose date/time of study drug in randomized control period.

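### The alternative primary endpoint does not say that only post-dose counts qualify, so the pre-dose Visit 2 count can serve as the first of the two consecutive counts; the effect is small and the SAP can close it

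*Protocol*

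**What the plan says.** **Eligibility.** Protocol 6.1.1, criterion 4, averages the Screening count and one other count taken within 28 days on either side of Screening. The average must be below 30×10⁹/L and neither count may exceed 35. For the second count a site "may use a historical value collected per standard of care if within 28 days of Screening". Protocol 9.1.2 adds: "The 2 samples must be obtained ≥24 hours and ≤28 days apart and the results must be available prior to randomization". Screening itself may be up to 28 days before Day 1 ("The Screening Visit must be completed within 28 days of Day 1/Visit 2").

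**Day 1.** Protocol 9.1.3 draws a local platelet count before randomisation and dosing. For the case introduced by "If the Visit 2 platelet count will not be 1 of the 2 platelet counts used to determine study eligibility", the only instruction is to collect the count and enter it in the eCRF.

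**Period.** Protocol 4.1.1.2 is headed "Treatment Period (Visit 2 Through Visit 14"). Table 7 sets Visit 2 among the treatment visits, although it labels it Baseline and gives it no week number. SAP 4.1 starts the Core Phase on the day of randomisation.

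**Endpoint.** Protocol 3.2 counts a subject for whom "at least 2 consecutive platelet assessments are" at or above 50 during the 12-week Treatment Period without rescue. Protocol 11.2.2 and SAP 3.2.1 use the same window. The efficacy methods table in SAP 7.4 uses only the last eight of the 12 weeks.

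**Baseline.** SAP 4.3.1: "In the efficacy analysis, baseline platelet count is the average of the platelet count obtained at the Screening Visit/Visit 1" and the other qualifying count. It is not the Day 1 count as such.

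**The concern.** A response endpoint should be built from counts taken after treatment has begun. Here the endpoint wording, the period boundary and the Day 1 rule together allow one that was not. A child at 50 or more on Day 1 and again at Visit 3 meets the definition with a single on-treatment count, while every other child needs two. Nothing in the efficacy baseline definition prevents this: because that baseline is an average of eligibility counts, a Day 1 count outside the pair is neither the baseline nor excluded as pre-dose.

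The conflicting eight-week window makes it worse in one respect. Two programmers working from the same SAP could derive different responder sets, and only one of those sets excludes Visit 2. At stake is the correct classification of a few children on an endpoint that is key secondary in this SAP and primary in the second one.

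**Working it through.** **1. Can a Day 1 count of 50 or more occur within the rules?** Screening may be 28 days before Day 1 and the other count 28 days before Screening, so the counts can be 28 and 28 + 28 = 56 days old. They are then exactly 28 days apart, which is allowed. This is the extreme case, not the usual one. If Visit 2 is one of the two counts, the limit of 35 rules out a value of 50. If it is not, no limit is stated. So the gap exists only when Visit 2 is outside the pair.

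**2. Can that count enter an endpoint?**

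- Primary (durable) endpoint: SAP 7.4 uses Weeks 5 to 12. Visit 2 cannot enter.
- Alternative primary, protocol 3.2 and 11.2.2 and SAP 3.2.1: whole Treatment Period, no restriction to post-dose counts. Visit 2 can enter.
- Alternative primary, SAP 7.4 methods table: last eight weeks. Visit 2 cannot enter, but the definition differs from the other three places and is not listed in SAP 5.1 as a change from the protocol.
- Percentage of weeks: the denominator is weeks on treatment, up to 12, which matches Visits 3 to 14. Visit 2 does not appear to be used.
- Day 8 response: uses the Day 8 count only.

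The alternative primary endpoint is therefore the only one into which the Day 1 value itself can be read.

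**3. The plan's own power.** Exact enumeration of 54 versus 18 subjects with the two-sided Fisher test at 0.05 gives 94.5% for 41.3% versus 3.4% (stated: at least 90%) and above 99.9% for an 80-point difference (stated: at least 99%). Both statements reproduce.

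**4. How many children would be affected?** The documents give no distribution of Day 1 counts, so this step is an assumption. Model: log-normal counts with median 20, 25 or 30, between-child SD 0.5 or 0.8 and within-child SD 0.3 or 0.7 on the log scale, independent visits, no drug effect and no remission. Select children whose two counts average below 30 with neither above 35. Then draw Day 1 and 12 weekly counts. A child is an extra responder if Day 1 and Week 1 are both at least 50 and no consecutive pair within Weeks 1 to 12 qualifies.

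- Day 1 count of at least 50: 0.6 to 15% of eligible children.
- Extra responders: about 0.03 to 1.3% (0.03 to 0.04% at the low end, 1.26% at the high end).
- Chance of at least one among 18 placebo children, 1 − (1 − p)¹⁸: for p = 0.0004, 0.7%; for p = 0.0126, 20.4%. Expected number at the high end: 18 × 0.0126 = 0.23.
- One placebo child is 1/18 = 5.6 percentage points, against 0% in the planning source.

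In the same model 0.5 to 22% of children meet the endpoint at Visits 3 to 14 without any drug. The scenario that gives 1.26% is the one that gives 22%, which is far from the planning rate of 0%, so the high end is pessimistic.

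**5. What would it do to the test?** Take a much larger assumed share f that responds in both arms whatever the treatment. Placebo rate = f, avatrombopag rate = f + (1 − f) × 0.80, difference = 0.80 × (1 − f).

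| f | Difference (points) | Fisher power |
|---|---|---|
| 0 | 80 | >99.9% |
| 2% | 78.4 | >99.9% |
| 5% | 76 | >99.9% |
| 10% | 72 | >99.9% |
| 20% | 64 | 99.9% |

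With equal rates of 5 to 40% in both arms, Fisher's type I error is 0.017 to 0.034, below 0.05.

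**The case against.** The best counter-argument is that no one would programme it this way. Visit 2 is called Baseline and carries no week number, the sample-size text describes the endpoint in terms of two consecutive weeks, and the methods table would exclude Visit 2 altogether. This makes exclusion the likely intention. It does not make it the stated rule: the formal definitions speak of assessments in a period that begins at Visit 2, and the table's window cannot serve as a safeguard while it contradicts SAP 3.2.1.

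A second argument is that eligibility is reviewed again at Visit 2 and the investigator may exclude an unsuitable child. That is true, but criterion 4 concerns the two averaged counts, and 9.1.3 expressly provides for a Day 1 count outside them.

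A third is that the inferential harm is negligible. That stands.

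A reader might infer more, and the documents do not support it:

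- **That a placebo responder is likely.** If 2%, 5% or 10% of children entered with a sustained count of 50 or more, the chance of at least one placebo responder would be 30%, 60% or 85%. Such children would also be at or above 50 at Visits 3 and 4 and would respond with or without Visit 2, so these figures do not measure this gap.
- **That the primary endpoint loses power.** A fall from 94.5% to 91.2% (2%) or 85.7% (5%) needs children who stay at 50 or more through Weeks 5 to 12. The Day 1 count is not what makes them responders.
- **That remission is frequent here.** The 62 to 74% figures in the protocol describe childhood ITP generally, not disease of at least six months with insufficient response to treatment.

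**Conclusion.** The point holds as a definitional gap with a small effect. As worded in protocol 3.2 and SAP 3.2.1, a pre-dose count can form half of a response on the alternative primary endpoint, and the SAP gives two incompatible windows for that endpoint. Under the assumed model about 0.03 to 1.3% of children would be reclassified, with a chance from under 1% to about 20% of at least one such child among 18 on placebo. These sizes rest on assumed distributions and independent visits; only the textual findings come from the documents. The bias acts in both arms and towards no difference.

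Two wider conclusions do not follow. The documents do not show that the enrolled population is wrong: a Day 1 limit would change who is enrolled, and the protocol describes its population as consistent with other paediatric trials of the class. Nor is the averaged efficacy baseline an error of inference. Change from baseline is a descriptive summary, and regression to the mean is expected equally in both randomised arms. Making Day 1 an eligibility count would not remove it, because Day 1 would then itself be a selected count.

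**What to change.** 1. Reconcile the alternative primary window in the SAP 7.4 methods table with SAP 3.2.1 and protocol 3.2. If a different window is intended, list it in SAP 5.1 as a change from the protocol.
2. State in the SAP that only scheduled post-dose assessments, from Visit 3 (Week 1) onward, count towards this endpoint. Use the term post-dose rather than post-baseline: the efficacy baseline is an average of earlier counts, so a Day 1 count outside the pair could be called post-baseline. Put the same sentence in the second SAP.
3. Optional: a sensitivity analysis of Day 8 response and the alternative primary in which children with a Day 1 pre-dose count of 50 or more are non-responders for early response.
4. Optional, if eligibility stays as it is: show platelet change from the Day 1 pre-dose local count beside change from the averaged baseline.

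All four are SAP text on data already collected, to be settled before database lock. Items 1 and 2 cost almost nothing; items 3 and 4 add a table or two. Whether a Day 1 platelet limit should apply before randomisation is a separate trade-off for the sponsor. It would need a local result before randomisation and would cause some further screen failures.

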9.1.4 Visit 3 (Week 1; Day 8 ±1 Day)

The following assessments will be performed during Visit 3:

- Perform WHO Bleeding Scale Assessment (Appendix C). The Investigator should ask the subject and/or the subject's parent/caregiver the following question: "Have you had any bleeding or bruising since I saw you last?". This assessment should be completed prior to other visit assessments.
- Collect vital signs (blood pressure, heart rate, and temperature). Vital signs should be taken after sitting for 5 minutes, whenever possible, and prior to any blood draws
- Collect blood for platelet count (local laboratory).

- Collect blood for sparse PK sample (Section 9.6) and record date/time of the last dose of study drug in the eCRF.
- Review study drug administration and Dosing Diary completion with the subject and/or the subject's caregiver.
- Record any AEs.
- Review and record any concomitant medications, including any modifications to or new concomitant ITP medications.
- Discharge subject from clinic with instructions for when to return for Visit 4.

